5.1.1. Primary Objective(s)

The primary endpoint is the incidence of subjects reporting serious adverse device effects (ADEs) up to and including the 30 day (+14 day) post-operative follow up visit including intra- and post-operative leaks. The causes of these leaks will be documented when available.

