9.7.2. Discharge Assessment

On the day of discharge the following assessments will be made:

- Procedure related adverse events
- Adverse device effects (e.g. air leak, anastomotic leak, staple line bleeding, peritonitis, sepsis, intracavitary infection, intervention or reoperation)
- Length of hospital stay
- Length of intensive care unit stay (if applicable)
- Surgical site and infection assessment by the Investigator according to the standard of care and site policy, ex. Positive wound culture
- Relevant concomitant medications (only those related to relevant medical history or adverse events will be collected e.g.: anticoagulants, blood pressure, antibiotics, pain medications)

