11.1.3. Adverse Device Effect (ADE)

In alignment with ISO 14155:2011 (Section 3.1), an Adverse Device Effect is an adverse event related to the use of an investigational medical device.

This definition includes adverse events resulting from insufficient or inadequate instructions for use, deployment, implantation, installation, or operation, or any deficiency/malfunction of the investigational medical device.

This definition includes any event resulting from use error or from intentional misuse of the investigational medical device.

Adverse Device Effects will be reported by the Investigator(s). If escalation is required (due to the potential need for reporting) ADEs will be reviewed by Medtronic Medical Affairs. Both confirmed and possible adverse device effect events will be included in the study report.

Examples of adverse device effects include but are not limited to: leaking or bleeding due to non-functional staple closure, damage to surrounding tissue due to unintentional firing, unintentional tissue loss due to reload locks on tissue

ADEs will be collected and documented at procedure and up to and including the 30-day follow-up visit.

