11.1.8. Adverse Event Relationship Classification

Causality assessments define the relationship between the use of the medical device (including the medical-surgical procedure) and the occurrence of each adverse event, according to MEDDEV (Guidelines on Medical Devices, Clinical Investigations: Serious Adverse Event Reporting). The presence of confounding factors, such as concomitant medication/treatment, the natural history of the underlying disease, other concurrent illness or risk factors shall also be considered.

Each AE will be classified according to five different levels of causality. The sponsor and the investigators will use the following definitions to assess the relationship of the serious adverse event to the investigational medical device or procedures:

MDT17025SIG Version 3.0 Page 41 of 57

Not related: relationship to the device or procedures can be excluded when:

- 1. the event is not a known side effect of the product category the device belongs to or of similar devices and procedures
- 2. the event has no temporal relationship with the use of the device or the procedures;
- 3. the serious event does not follow a known response pattern to the medical device (if the response pattern is previously known) and is biologically implausible;
- 4. the discontinuation of medical device application or the reduction of the level of activation/exposure when clinically feasible and reintroduction of its use (or increase of the level of activation/exposure), do not impact on the serious event;
- 5. the event involves a body-site or an organ not expected to be affected by the device or procedure;
- 6. the serious event can be attributed to another cause (e.g. an underlying or concurrent illness/clinical condition, an effect of another device, drug, treatment or other risk factors);
- 7. the event does not depend on a false result given by the device used for diagnosis, when applicable;
- 8. harms to the subject are not clearly due to use error;
- 9. In order to establish the non-relatedness, not all the criteria listed above might be met at the same time, depending on the type of device/procedures and the serious event.

Unlikely: the relationship with the use of the device seems not relevant and/or the event can be reasonably explained by another cause, but additional information may be obtained.

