Possible: the relationship with the use of the device is weak but cannot be ruled out completely. Alternative causes are also possible (e.g. an underlying or concurrent illness/ clinical condition or/and an effect of another device, drug or treatment). Cases were relatedness cannot be assessed or no information has been obtained should also be classified as possible.

Probable: the relationship with the use of the device seems relevant and/or the event cannot reasonably be explained by another cause, but additional information may be obtained.

Causal relationship: the serious event is associated with the device or with procedures beyond reasonable doubt when:

- 1. the event is a known side effect of the product category the device belongs to or of similar devices and procedures;
- 2. the event has a temporal relationship with device use/application or procedures;
- 3. the event involves a body-site or organ that
 - a. the device or procedures are applied to;
 - b. the device or procedures have an effect on;
- 4. the serious event follows a known response pattern to the medical device (if the response pattern is previously known);

MDT17025SIG Version 3.0 Page 42 of 57

- the discontinuation of medical device application (or reduction of the level of activation/exposure) and reintroduction of its use (or increase of the level of activation/exposure), impact on the serious event (when clinically feasible);
- 6. other possible causes (e.g. an underlying or concurrent illness/ clinical condition or/and an effect of another device, drug or treatment) have been adequately ruled out;
- 7. harm to the subject is due to error in use;
- 8. the event depends on a false result given by the device used for diagnosis, when applicable;
- 9. In order to establish the relatedness, not all the criteria listed above might be met at the same time, depending on the type of device/procedures and the serious event.

The Sponsor and the Investigators will distinguish between the serious adverse events related to the device and those related to the procedures (any procedure specific to the clinical investigation). An adverse event can be related both to procedures and the device. Complications of procedures are considered not related if the said procedures would have been applied to the subjects also in the absence of device use/application.

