In some particular cases the event may be not adequately assessed because information is insufficient or contradictory and/or the data cannot be verified or supplemented. The sponsor and the Investigators will make the maximum effort to define and categorize the event and avoid these situations. Where the sponsor remains uncertain about classifying the serious event, it should not exclude the relatedness and classify the event as "possible".

Particular attention shall be given to the causality evaluation of unanticipated serious adverse (device) events. The occurrence of unanticipated events related to the use of the device (USADE) could suggest that the clinical investigation places subjects at increased risk of harm than was to be expected beforehand

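### Does the primary endpoint need a stated causality cut-off before a serious leak of unknown cause can be counted?

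*Protocol*

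**What the plan says.** Protocol 5.1.1 defines the primary endpoint as the incidence of subjects with serious adverse device effects "up to and including the 30 day (+14 day) post-operative follow up visit including intra- and post-operative leaks". It adds of those leaks: "The causes of these leaks will be documented when available". SAP 4.1 has the same definition.

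Protocol 11.1.3 defines an ADE as an adverse event related to use of the device, and 11.1.4 defines a SADE as an ADE with serious consequences. Four further statements bear on what counts as related:

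- 11.1.8, the scale: "Each AE will be classified according to five different levels of causality". The levels are not related, unlikely, possible, probable and causal relationship.
- 11.1.8, the default: "Cases were relatedness cannot be assessed or no information has been obtained should also be classified as possible".
- 11.1.8, where the sponsor is uncertain about a serious event: "it should not exclude the relatedness and classify the event as" possible.
- 11.1.3, on reporting: "Both confirmed and possible adverse device effect events will be included in the study report".

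The analysis sections, Protocol 13.4.1 and SAP 7.9, name the endpoint and a two-sided 95% confidence interval but no causality threshold. Protocol 13.4.1 sets the acceptance criterion: an upper limit below 20%.

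**The concern.** Three features make the numerator look loosely defined.

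**No stated cut-off.** Five levels are recorded, but no sentence says which of them make an event device-related for the endpoint. Leak causes are recorded only when known, so a serious leak of unknown cause is the obvious test case.

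**Leak examples that differ.** Protocol 9.7.2 has "Adverse device effects (e.g. air leak, anastomotic leak, staple line bleeding, peritonitis, sepsis, intracavitary infection, intervention or reoperation", with no condition on cause. Protocol 11.1.3 has "leaking or bleeding due to non-functional staple closure", which does carry one.

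**Uneven wording.** Leaks are named in Protocol 5.1.1 and 13.2 and in SAP 4.1 and 6, but not in the Synopsis, Protocol 5.1, 9.7 and 13.4.1, or SAP 4 and 7.9. Protocol 5.1 and SAP 4 abbreviate the endpoint as ADEs and cite 11.1.3, whereas SAP 4.1 writes SADEs, the term defined in 11.1.4.

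The study is open-label and expects very few events. If one or two are rated only possible, they could be the whole numerator, and a counting rule settled after the data are seen would decide the reported rate.

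**Working it through.** **1. Reading the text for the test case.** Take a serious leak with no documented cause.

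- How is it rated? Under the two 11.1.8 defaults it is rated possible.
- Is a possible event an ADE for reporting? 11.1.3 says so.
- Does that reach the endpoint? Protocol 5.1 and SAP 4 state the objective in terms of serious adverse device effects and send the reader to 11.1.3, which holds the sentence on confirmed and possible events. The link is implicit, but it is there.

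The resulting rule is that possible, probable and causal events count, and unlikely and not related do not.

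**2. The leak examples.** Both lists are open-ended (9.7.2 gives examples in a visit checklist; 11.1.3 says its list is not exhaustive). Both illustrate the term ADE, which already requires relatedness to the device. A leak enters the endpoint only if it is serious and device-related, whether or not a section names leaks.

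**3. The label.** Each endpoint statement spells out serious adverse device effects in full. Only the bracketed abbreviation varies.

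**4. The plan's own figures.** Protocol 13.2 and SAP 6 use ADE rates of 3.3% (abdominal, 53), 2.5% (thoracic, 74) and 2.9% (overall, 127), with 5% attrition. With mean m = 0.95 × N × p, P(at least 1) = 1 − exp(−m):

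| Group | m | P(at least 1) | Stated |
|---|---|---|---|
| Abdominal | 0.95 × 53 × 0.033 = 1.66 | 81.0% | 81% |
| Thoracic | 0.95 × 74 × 0.025 = 1.76 | 82.8% | 83% |
| Overall | 0.95 × 127 × 0.029 = 3.50 | 97.0% | 97% |

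Overall P(at least 2) = 1 − exp(−m)(1 + m) = 86.4%, stated as 86%. All four reproduce, and none depends on the causality cut-off.

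**5. What the cut-off could move.** Expected ADEs before attrition are 53 × 0.033 = 1.75 and 74 × 0.025 = 1.85. These cover ADEs of any seriousness, so at the planning rates they are upper bounds for SADEs. The documents do not say how many events would be rated only possible; I assume 0 to 3 per arm. No interval method is named; I assume the exact (Clopper-Pearson) limit, whose upper bound for x events in n is the 97.5% quantile of Beta(x+1, n−x).

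| Events | Thoracic (n=74): rate, upper limit | Abdominal (n=53): rate, upper limit |
|---|---|---|
| 0 | 0%, 4.9% | 0%, 6.7% |
| 1 | 1.4%, 7.3% | 1.9%, 10.1% |
| 2 | 2.7%, 9.4% | 3.8%, 13.0% |
| 3 | 4.1%, 11.4% | 5.7%, 15.7% |

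Counting two events rather than none about doubles the upper limit, but every entry is below 20%.

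**6. Where the decision would turn.** The largest passing counts are 7/74 (upper limit 18.5%; 8/74 gives 20.2%) and 4/53 (18.2%; 5/53 gives 20.7%). The binomial probability of staying at or below them at the planning rates is 99.95% thoracic and 97.0% abdominal. After 5% attrition the maxima are 7/70 and 4/50, with probabilities 99.96% and 97.6%. Because SADEs are a subset of ADEs, these are lower bounds at those rates. The Wilson interval gives the same maxima except at n=74, where 8 events also pass.

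**The case for a change.** The strongest case for a change is that being rated and being reported are not the same as being counted. Inclusion in a study report could mean a listing. The word confirmed in 11.1.3 is not one of the five levels, so its mapping to probable or causal is left to the reader. A further sentence in 11.1.8 treats complications of procedures that would have been done anyway as unrelated, which could pull a leak the other way. Investigators and sponsor both classify events and the Independent Medical Monitor (Protocol 12.2) adjudicates prespecified ones, yet no rule says whose rating is final. The study is unblinded, the interim analysis at 64 subjects supports a regulatory submission, and the clarification would need no new data.

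Much of this is true as description: neither 13.4.1 nor SAP 7.9 writes the rule down or names the final assessor. It does not show that two careful analysts would count differently. The 11.1.8 defaults resolve uncertainty towards relatedness, and 11.1.3 keeps possible events in. Under either mapping of confirmed, probable and causal events are included. SAP 7.10 already reports adverse events by relation to the device and by seriousness, and lists SADEs with those characteristics, so an omission from the numerator would be visible. One sentence in SAP 7.9 would be tidy, but it would only record what the protocol implies.

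**Conclusion.** No change is called for. This is missing detail that analysts fill sensibly from 11.1.3 and 11.1.8, together with editorial variation in how leaks and the SADE abbreviation appear. The numerator implied by the text is subjects with at least one serious event rated possible, probable or causal in relation to the device.

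The most the omission could do is move the reported rate and its upper limit: for two events rather than none, from 0% to 2.7% (thoracic) or 3.8% (abdominal), with the upper limit rising from 4.9% to 9.4% or from 6.7% to 13.0%. The conclusion against 20% is not expected to change. This rests on the planning ADE rates holding as upper bounds for SADEs, on an exact interval, and on no more than 3 events per arm rated only possible. If true rates were far above the planning values, a single event could matter at the boundary (4 versus 5 of 53, or 7 versus 8 of 74), but the default in 11.1.8 would still say how to rate an event that cannot be assessed.

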5.1.2. Secondary Objective(s)

The secondary endpoint is device deficiency/malfunction affecting the intended performance of the device to include;

MDT17025SIG Version 3.0 Page 19 of 57

- Staple line assessment:
 - o Intraoperative assessments:
 - Assessment of staple line integrity
 - Incidence of staple line bleeding (measured as ≥ 50 cc)
 - Additional intervention(s) to treat staple-line failure (ex: glue, manual over sew,
 Medtronic buttress) or intraoperative revision/recreation of the anastomosis
 - Incidence of leakage (as measured by air leak test, or standard of care, as applicable)
 - Post-operative assessments:
 - Duration of air leakage (in days) for thoracic procedures
 - Prolonged air leaks are considered >7 days
 - Incidence of leakage for abdominal procedures as evidenced confirmed by imaging subject presentation or decline in status, or need for reoperation/reintervention
 - Incidence of post-operative infection, assessed by the Investigator according to the standard of care and site policy, ex. positive wound culture
 - Additional intervention(s) to treat staple-line failure
- Incidence of repeat hospital admissions for primary procedure-related complications.

All recorded device deficiencies/malfunctions will be captured and assessed by the Investigator. Complaints will be handled in accordance with the standard procedures for the post-market vigilance system.

6. Study Design

The purpose of this study is to confirm the safety and performance of the Signia[™] Stapling System with Endo GIA[™] with Tri-Staple[™] Technology and Tri-Staple[™] 2.0 Intelligent Reloads in a minimum of 127 enrolled subjects undergoing indicated abdominal or thoracic procedures enrolled at approximately 10 sites in the USA and Europe (potentially in the United Kingdom, Spain, Italy).

6.1. Duration

Including enrollment/screening and follow-up time for all enrolled subjects the study is estimated to progress for up to 24 months. Not including hospital stay (which could vary depending on the procedure), subjects will participate for potentially 74 days. Screening for eligibility may occur 30 days (inclusive) prior to the procedure. Post-procedure, subjects will be assessed for incidence of adverse device effect events up to and including the 30 day (+14 day) post-operative follow up visit.

MDT17025SIG Version 3.0 Page 20 of 57

6.2. Rationale

In order to assess the clinical safety of the Signia™ Stapling with Endo GIA™ with Tri-Staple™ Technology and Tri-Staple™ 2.0 Intelligent Reloads, Medtronic is performing a prospective, two-arm, multicenter, post-market study on adult subjects undergoing abdominal or thoracic procedures using the device and appropriate Reloads (See Appendix A). During the procedure device deficiencies affecting the intended performance of the device will be collected and incidence of reported adverse device effects will be assessed up to and including the 30 day (+14 day) post-operative follow up visit following the procedure. This study does not utilize any randomization or blinding. Currently there are no known factors that may compromise study outcomes or the interpretation of results (e.g., baseline characteristics, concomitant medications, the use of other study products, or subject-related factors such as age, gender or lifestyle). If any adverse device effect occurrences are identified they will be assessed, reported and documented in the eCRF.

6.3. Selection of Investigators

Surgeons who are qualified by training (board certified in abdominal and/or thoracic procedures in accordance with USA/European and hospital guidelines), education, and relevant experience appropriate to the use of the product and associated procedures will be considered for participation as investigators in this study. Investigators/sites must have adequate time and resources to conduct the study throughout the duration of the study and have access to an adequate number of eligible subjects. Investigators/sites must be able to comply with applicable Institutional Review Board (IRB)/Ethics Committee (EC) and regulatory requirements. Investigator must not be debarred, disqualified, or working under sanctions in applicable regions. Qualifications are verified through valid Curriculum Vitae (CV) and current licensing. Current license (USA only) and CVs will be maintained with study documentation.

The Investigators and the associated clinical study staff will receive training on the management of the clinical study and the device according to the instructions for use (IFU).

7. Product Description

7.1. General

The Signia™ stapler is a reusable intelligent surgical stapler that provides push-button powered maneuverability and delivery of compatible stapling reloads. The Signia™ Stapling System is the combination of the Signia™ stapler and system accessories.

[figure not shown]
The Signia[™] stapler is composed of the Signia[™] power handle, Signia[™] power shell, and Signia[™] adapters. The system accessories include a reusable insertion guide, a manual retraction tool, a single-bay charger. The Signia[™] stapler is compatible with Endo GIA[™] single-use reloads, Endo GIA[™]

MDT17025SIG Version 3.0 Page 21 of 57

single-use reloads with Tri-Staple™ Technology, Tri-Staple™ 2.0 single-use reloads, and Signia™ Intelligent Loading Units with Tri-Staple™ 2.0 single-use Reloads (see appendix A for Reloads to be assessed in this study).

7.1.1. Signia™ Stapler

[figure not shown]
7.1.1.1. Signia™ Power Handle

The Signia™ power handle is a non-sterile reusable, battery-powered stapling handle that includes microprocessors, electronics, motors, an OLED display screen, and a rechargeable lithium (Li)-ion battery.

The Power Handle provides instrument intelligence (software) and contains a microprocessor, that controls supporting electronics, and motor assemblies for rotation, articulation, jaw open/close and firing of compatible stapling reloads. The control of the reloads is provided by three motor assemblies in the handle, and then delivered to the attached Linear Adapter through multiple drive shafts to deploy the compatible reloads.

The "Intelligence Enabled" symbol is a trademarked symbol originated by Medtronic that is used in the branding of Signia™ Stapling products. It means that the product contains an ID-enabled IC chip. The chip will have the ability to communicate with compatible Signia™ stapling products that also have an ID-enabled IC chip.

MDT17025SIG Version 3.0 Page 22 of 57

7.1.1.2. Signia™ Power Shell

The Signia[™] power shell is a single-use, sterile shell that covers the non-sterile Signia[™] power handle to create an aseptic barrier, control interface, and universal adapter connector. It also provides a communications interface for Tri-Staple[™] 2.0 single-use reloads and Signia[™] Intelligent Loading Units with Tri-Staple[™] 2.0 single-use Reloads indicated for use with the Signia[™] stapler.

7.1.1.3. Signia™ Linear Adapter(s)

The Signia™ linear adapters (short, standard and XL) are non-sterile reusable instruments that attach to the stapling handle to enable functionality of compatible stapling reloads. Included are motor mating connectors, electronic sensors, and communications interfaces for Tri-Staple™ 2.0 single-use reloads and Signia™ Intelligent Loading Units with Tri-Staple™ 2.0 single-use Reloads indicated for use with the Signia™ stapler. It is provided non-sterile and must be cleaned and sterilized prior to each use as per the instructions for use.

7.1.2. Signia™ Accessories

7.1.2.1. Signia™ Reusable Insertion Guide

The Signia™ reusable insertion guide is used to help maintain the sterility of the power shell during insertion of a non-sterile Signia™ power handle. It is provided non-sterile and must be cleaned and sterilized prior to each use as per the instructions for use.

[figure not shown]
7.1.2.2. Signia™ Manual Retraction Tool

The Signia™ manual retraction tool is a reusable, handheld device that can be used to operate the adapter controls in the event of a malfunction during operation. The tool can be used to complete a firing, retract the knife and open the jaws, and/or articulate a stapling reload. It is provided non-sterile and must be cleaned and sterilized before use as per the instructions for use.

